5.3. Participant Re-Screening

Participants who screen fail may be rescreened as long as the participant was not a screen fail due to noncompliance with the protocol (ie, positive urine drugs of abuse screen, etc). If the participant is re-screened, the participant must again consent to participate in the study and a new Screening number must be used. All Screening assessments will be repeated.

5.4. Participant Withdrawal

Participants are free to discontinue the study at any time, for any reason, and without prejudice to further treatment. The Investigator may remove a participant if, in the Investigator's judgment, continued participation would pose unacceptable risk to the participant or to the integrity of the study data. All procedures for the ET Visit must be completed. Reasons for removal or withdrawal may include:

- Withdrawal of consent
- Discretion of the Investigator/Sponsor
- Participant noncompliance
- Safety concern by the Investigator or the Sponsor

Once dosed, participants who discontinue the study due to an AE will not be replaced. Participants who discontinue the study due to reasons other than an AE or who have non-evaluable PK samples may be replaced at the discretion of the Sponsor.

In the event of a participant's withdrawal, the Investigator will promptly notify the Medical Monitor and Study Director and will make every effort to complete the Early Termination (ET) assessments. All withdrawn participants with ongoing clinically significant AEs/serious adverse events (SAEs) or laboratory findings will be followed until the finding is resolved or medically stable; reasonable attempts will be made to follow-up with participants.

5.5. Early Termination of Study

The Sponsor has the right to terminate this study at any time. Reasons for terminating the study may include, but are not limited to, (1) the incidence or severity of AEs in this or other studies indicating a potential health hazard to participants, and (2) in the Sponsor's judgment, there are no further benefits to be achieved from the study.

If the study is terminated early, the Sponsor shall inform all Investigators/institutions, regulatory authorities, and the Institutional Review Board (IRB).

5.5.1. Stopping Rules

All participants will be closely monitored for any AEs by the site Investigator and the Sponsor's Medical Monitor. The SMC will meet to review the Day 42 PK data as well as safety and tolerability data prior to the first and second dose escalations in the multiple ascending dose period of the study. Additionally, the SMC will meet on an ad hoc basis under any condition(s) where decisions about ongoing participant dosing in the study is in question and participant safety may be at risk. Criteria that may warrant an ad hoc SMC meeting include, but are not limited to the following:

1. A participant experiences any AE Grade ≥ 2 or SAE.
2. A participant experiences worsening of an ongoing AE by ≥ 1 grade.
3. A participant experiences any other finding (symptoms, physical examination, laboratory) whose severity may preclude dosing new participants in the study.

AEs will be graded based on National Cancer Institute's Common Toxicity Criteria Scale (NCI CTCAE v5). The individual participant's tolerability to the study drug will be determined based on the criteria provided below. Individual Dose Stopping Rules

Dosing for any individual participant will be stopped if the participant experiences a SAE or a clinically significant nonserious AE, which in the opinion of the Principal Investigator or Sponsor's Medical Monitor, warrants discontinuation of the study for that participant's well-being.

5.6. Safety Monitoring Committee

The sites' Principal Investigators and the Sponsor's Medical Monitor will closely monitor the safety of the study participants throughout the duration of study. The SMC will review the totality of safety, tolerability, and available PK and PD data to monitor safety.

The SMC will be composed of the Principal Investigators from each site, or designee, and Sponsor representatives, including the Medical Monitor, Clinical Pharmacologist, Biostatistician, and Product Safety Officer and/or Product Safety Medical Scientist. The SMC will have overall responsibility for any safety and tolerability decisions and for proceeding with dose escalation. Details of the scope including decision, responsibilities, action taken, and frequency of the SMC will be provided in the SMC charter.

In the Multiple Ascending-dose Period of the study, the SMC will review safety, tolerability, PK, and PD data through Day 42 after the single dose from at least 4 participants. The Sponsor will inform the SMC in writing regarding the GBT021601 half-life, and dosing interval of steady-state multiple dosing for the participants of this study.

For the Extended treatment period (Part C), the SMC will meet on an ad hoc basis under any condition(s) where decisions about ongoing participant dosing in the study is in question and participant safety may be at risk.

This is an open label study, so the data reviewed to make dose escalation decisions will not be blinded.

5.7. Dose Escalation Criteria

The % Hb occupancy by GBT021601 will be calculated from the PK as the ratio of GBT021601 concentration to the Hb (estimated at 5mM) in RBCs. The Hb% modification will be based on hemoximetry data. The Hb% occupancy/modification will be utilized as a PD marker because it is a measure of target engagement that has been employed in prior clinical studies of hemoglobin modifying agents.

Dose escalation will be pharmacologically guided (based on PK and PD target levels, [Table 6](#)). Dose escalation will proceed after review of safety, tolerability, PK, and PD data through Day 42. Dose escalation will stop according to the stopping rules (Section [5.5.1](#)). Dose escalation will proceed (no more than 2-fold increments) beginning with the Dose 1 with a predicted target of ~20% to 30% Hb occupancy/modification and Dose 2 with a predicted target of > 30% Hb occupancy/modification.

Concerns over potential acute mechanism-related toxicities (tissue hypoxia) are related to the peak achieved % Hb occupancy and therefore to the maximum plasma concentration (C_{max}). For this reason, prior to initiating multiple doses, safety, tolerability, PK, and PD data will be reviewed by the SMC. Prior to dose escalation, dose levels may be revised if indicated, based on PK/PD data.

Progression to the next higher dose will only occur if the previous dose level was deemed by the SMC to be safe and well tolerated.

When it is not appropriate to escalate the dose, then the same dose or a titrated dose may also be investigated depending upon the results of the safety data from the previous dose levels.

Table 6: Target % Hb Occupancy/Modification for Multiple Ascending-dose Period, Intrapatient Dose Escalation

Dose Escalation Level	Predicted % Hb Occupancy/Modification	Anticipated Loading Dose (mg) ^a	Anticipated Maintenance Dose (mg) ^a
Dose 1	~20% to 30%	TBD	TBD every TBD
Dose 2	> 30%	TBD	TBD every TBD

^a The GBT021601 dose levels and frequency to be evaluated will be determined based on PK/PD evaluation of single doses in healthy volunteers and Day 42 PK in adults with SCD.

Based on the findings from Dose Levels 1 and 2, there were no significant safety concerns related to GBT021601 and based on PPK modeling, the planned doses are expected to result in Hb occupancy of approximately 54%.

Table 7: Model-Predicted Dose Planned for Extended Treatment Period

Loading Dose	Maintenance Dose	Mean Targeted % Hb Occupancy
300 mg BID x 4 days	150 mg QD	~54%

6. TREATMENT OF PARTICIPANTS

6.1. Description of Study Drug

Study drug details are presented in [Table 8](#).

Table 8: Identity of Study Drugs

Study Drug	Dosage Form	Strength
GBT021601	Tablet	100 mg
GBT021601	Capsule	5 mg, 25 mg

As of Protocol Amendment 5, study drug will be provided as a tablet or capsule as per [Table 9](#).

Table 9: Study Drug for Extended Treatment Period

Study Drug	Dosage Form	Dose Strength
GBT021601	Tablet	100 mg
GBT021601	Capsule	25 mg

GBT021601 tablets and capsules will be provided by the Sponsor.

6.2. Treatments Administered

Study drug will be administered orally with approximately 240 mL non-carbonated room temperature water.

6.3. Method of Assigning Participants to Treatment Groups

This is an open-label, single-arm, intrapatient, single dose and multiple dose escalation study. Participants will be assigned a study identification number during Screening and a separate number assigned at enrollment.

6.4. Measurements of Treatment Compliance

The first dose of the study drug will be administered by delegated and trained staff at the clinical research unit (CRU). Details regarding dosing, including the dose administered and the date and time of dosing, will be recorded in a dosing diary during the maintenance doses. Additionally, a hand and mouth check will be performed to verify that the administered dose was swallowed.

For the Multiple Ascending-dose Period of this trial, at Week 8 and Week 13 Visits, the loading dose (as applicable) will be administered by delegated and trained staff at the CRU. Details regarding dosing, including the dose administered and the date and time of dosing, will be recorded. Maintenance doses will be administered either by the CRU staff during visits or by the participant based on the to be determined frequency of dosing. Recording of dosing to monitor compliance will also be based on the dosing frequency.

6.5. Concomitant Medications, Procedures, Other Restrictions and Requirements

6.5.1. Concomitant Medications and Procedures

Study participants will be allowed to take other medications as needed with the exception of those described listed in Section [6.5.2](#). All concomitant medications will be documented.

In the interests of participant safety and acceptable standards of medical care the Investigator will be permitted to prescribe treatment(s) at his/her discretion. All treatments must be recorded in the participants' electronic case report form (eCRF) (medication, dose, treatment duration and indication).

6.5.2. Other Restrictions

Participants will be instructed to adhere to the following restrictions:

- Participants are not permitted to use drugs of abuse from Screening through EOS/ET Visit.
- Participants are not permitted to use herbal preparations or dietary supplements, or any drugs that induce or inhibit study drug-specific CYP(s) within 14 days or 5 half-lives, whichever is longer, prior to Day -1.
- Participants are not permitted to use voxelotor, crizanlizumab, or L-glutamine while participating in this clinical study.
- Participants are not permitted to consume grapefruit and/or grapefruit juice from 14 days prior to Day -1 through the EOS/ET Visit.
- During the Single-dose Period, participants are not permitted to consume any food and drink from outside of the CRU while residing at the CRU.
- Participants are not permitted to participate in any other interventional clinical study or donate blood or plasma while participating in this clinical study.

6.5.3. Fertility and Contraceptive Requirements

6.5.3.1. Female Participants of Childbearing Potential

Refer to Inclusion Criterion [6](#).

Female participants who are of child-bearing potential are required to use highly effective methods of contraception.

Highly effective contraception methods are defined as the following:

- a. Estrogen and progestogen containing hormonal contraception associated with inhibition of ovulation OR progestogen only hormonal contraception associated with inhibition of ovulation by oral, implantable, or injectable route of administration
- b. An intrauterine device (IUD)
- c. An intrauterine hormone-releasing system (IUS)

- d. Females with bilateral tubal occlusion
- e. Surgically sterile male partner (eg, vasectomy)
- f. True sexual abstinence, defined as refraining from heterosexual intercourse during the entire period of risk associated with the study treatments. Periodic abstinence (eg, calendar, ovulation, symptom-thermal, post-ovulation methods), and withdrawal are not acceptable methods of contraception.

6.5.3.2. Instructions for Male Participants Capable of Fathering a Child

There is no information about effects that GBT021601 could have on male sperm and on the development of the fetus in humans. Therefore, it is important that the female partners of male participants do not become pregnant during the study and for a total period of 165 days after the male participant has taken the last dose of GBT021601.

As a precaution, all male participants who are sexually active and not surgically sterile should avoid fathering a child by either true abstinence or the use of barrier methods of contraception plus highly effective contraception for their female partner if of childbearing potential.

6.5.3.3. Acceptable Forms of Contraception for Male Participants with Female Partners Capable of Reproduction

Refer to Inclusion Criterion 6.

Male participants who are not surgically sterile with partners of childbearing potential must agree to use a highly effective method of birth control during the study and for 165 days after the last dose of study drug. A highly effective method of contraception is defined as one that results in a low documented failure rate when used consistently and correctly such as: condom plus use of an intrauterine device; intrauterine system or hormonal method of contraception (oral, injected, implanted, or transdermal) for their female partner; or sexual abstinence.

Male participants who are not surgically sterile with a partner who is pregnant must agree to condom use or maintain sexual abstinence during the study and for 165 days after the last dose of study drug.

7. STUDY DRUG MATERIALS AND MANAGEMENT

7.1. Study Drug

GBT021601 will be provided as a tablet formulation in the strength of 100 mg and a capsule formulation in strengths of 5 mg and 25 mg. All excipients used are compendial grade and are listed in the FDA's Inactive Ingredients Database. As of Protocol Amendment 5, GBT021601 will be provided as a 100 mg tablet or a 25 mg capsule.

7.2. Study Drug Packaging and Labeling

GBT021601 will be provided in high density polyethylene (HDPE) bottles of 30 tablets and in separate HDPE bottles of 30 capsules with child resistant caps with induction seal and labeled according to local regulations.

7.3. Study Drug Storage

Study drug will be stored at controlled room temperature between 15°C to 25°C in the storage area of the investigational site pharmacy, which is a secure, temperature controlled, locked environment with restricted access.

No special considerations for safe handling of GBT021601 are required.

7.4. Blinding of Treatment Assignment

Not applicable since this is an open-label study.

7.5. Administration

GBT021601 will be administered orally. For the single-dose period, participants will fast at least 10 hours before and for at least 4 hours after study drug administration. Water will be allowed as desired except for 1 hour before and 1 hour after study drug administration.

For the multiple ascending-dose period of the study, GBT021601 can be taken with or without food.

Each dose will be administered orally with approximately 240 mL of water (additional water to complete dosing is allowed). Participants will be instructed to swallow the tablets or capsules within 5 minutes. If the participant vomits, the dose should not be repeated.

7.6. Study Drug Accountability and Disposal

The Investigator must ensure that all study drug supplies are kept in a secure locked area with access limited to those authorized by the Investigator. The Investigator must maintain accurate records of the receipt of all study drug shipped by the Sponsor or their representative, including but not limited to the date received, lot number, amount received, and the disposition of all study drug. Current dispensing records will also be maintained including the date and amount of study drug dispensed and the participant receiving the study drug. All remaining study drug not required by regulations to be held by the CRU must be reconciled prior to destruction. Drug may be returned to the Sponsor's representative immediately after the study is completed or destroyed on-site with Sponsor approval.

8. PHARMACOKINETIC AND PHARMACODYNAMIC ASSESSMENTS

8.1. Blood Sample Collection

The PK/PD samples for GBT021601 will be collected at time points specified in the PK/PD sampling schedules ([Table 1](#), [Table 2](#), [Table 3](#), and [Table 4](#)). Sample collection, processing, and shipping details will be outlined in a separate study reference manual.

For procedures scheduled to be performed at the same time, priority is to be given to collection of the PK samples at the designated time. ECGs, followed by vital signs, are to be performed before PK sampling unless PK samples will be delayed as a result.

8.1.1. Single-dose Period

During the Single-dose Period, plasma and whole blood PK samples will be collected at the following times:

Pre-dose (within 60 minutes of dosing) and postdose at 0.25, 0.5, 1, 2, 4, 6, 8, 12 hours; 24 hours (Day 2), 36 hours, 48 hours (Day 3), and 72 hours (Day 4); Days 7, 14, 21, 28, and 42.

The windows for sample collection are provided in [Table 10](#).

Table 10: Windows for PK Sample Collection – Single-dose Period

Sample Collection Time	Allowed Deviation
0.0 – 1.0 hour	± 2 minutes
> 1.0 – 24.0 hours	± 5 minutes
> 24.0 – 72.0 hours	± 10 minutes
> 72.0 – 144.0 hours	± 15 minutes
> 144.0 hours	± 24 hours

Blood samples for hemoxygometry and RBC deformability, dense cells will be collected at the same time as the PK samples at pre-dose and 12 hours postdose on Day 1. In addition, hemoxygometry samples will be collected on Days 2, 4, 7, 21, and 42.

8.1.2. Multiple Ascending-dose Period

Plasma and whole blood pre-dose and postdose PK samples will be collected in the Multiple Ascending-dose period as listed in [Table 11](#). Whole blood samples for hemoxygometry and RBC deformability, dense cells will be collected at the same time as the PK samples.

Table 11: PK and PD Sample Collection Times – Multiple Ascending-dose Period

Week	Pre-dose ^a	Postdose
8	1 PK/PD sample Pre-dose	1 PK sample between 0.25 hour to 1 hour 1 PK/PD sample between 2 to 4 hours
9	1 PK/PD sample Pre-dose	1 PK sample between 0.25 hour to 1 hour 1 PK/PD sample between 2 to 4 hours
10	1 PK/PD sample Pre-dose	1 PK sample between 0.25 hour to 1 hour 1 PK/PD sample between 2 to 4 hours
11	1 PK sample Pre-dose	1 PK sample between 0.25 hour to 1 hour, 1 PK/ sample between 2 to 4 hours
12	1 PK sample Pre-dose	1 PK sample between 0.25 hour to 1 hour 1 PK sample between 2 to 4 hours
13	1 PK/PD sample Pre-dose	1 PK sample between 0.25 hour to 1 hour 1 PK/PD sample between 2 to 4 hours
14	1 PK sample Pre-dose	1 PK sample between 0.25 hour to 1 hour 1 PK sample between 2 to 4 hours
15	1 PK sample Pre-dose	1 PK sample between 0.25 hour to 1 hour 1 PK sample between 2 to 4 hours
16 EOT	1 PK/PD sample Pre-dose	1 PK sample between 0.25 hour to 1 hour 1 PK/PD sample between 2 to 4 hours
EOS/ET	Anytime during visit	

Abbreviations: PD, pharmacodynamics; PK, pharmacokinetics.

^a The pre-dose blood sample for PK and PD assessments should be collected within 30 minutes prior to dosing.

Table 12: PK and PD Sample Collection Times –Extended Treatment Period CCI

Extended Treatment Period		Pre-dose ^a	Postdose
Week	Day		
1	1	1 PK/PD sample	1 PK sample between 0.25 hour to 1 hour 1 PK/PD sample between 2 to 4 hours
2	15	1 PK/PD sample	1 PK sample between 0.25 hour to 1 hour 1 PK/PD sample between 2 to 4 hours
4	29	1 PK sample	1 PK sample between 0.25 hour to 1 hour 1 PK sample between 2 to 4 hours
6	43	1 PK sample	1 PK sample between 0.25 hour to 1 hour 1 PK sample between 2 to 4 hours
10	71	1 PK sample	
14	98	1 PK sample	
Final Visit	Anytime during visit		

Abbreviations: PD, pharmacodynamics; PK, pharmacokinetics.

^a The pre-dose blood sample for PK and PD assessments should be collected within 30 minutes prior to dosing.

8.2. Pharmacokinetic Analysis

Plasma and whole blood concentrations will be determined using a validated assay.

For the single-dose period, the following whole blood, plasma, and PK parameters of GBT021601 will be calculated, if appropriate: maximum observed plasma/whole blood concentration (C_{max}), time of maximum serum concentration (t_{max}), area under the concentration vs time curve from zero to 24 hours (AUC_{0-24}), area under the concentration vs time curve from time zero to last quantifiable concentration (AUC_{0-t}), area under the concentration vs time curve from time zero extrapolated to infinity ($AUC_{0-\infty}$), apparent clearance (CL/F), apparent volume of distribution during the terminal phase (Vz/F), and half-life ($t_{1/2}$).

For the multiple ascending-dose period, the following whole blood and plasma PK parameters of GBT021601 will be calculated using nonlinear mixed effects modeling: plasma/whole blood C_{max} , plasma/whole blood C_{min} , plasma/whole blood AUC at steady-state and half-life. The % Hb occupancy will be estimated based on C_{min} and C_{max} as well as hemoximetry data.

8.3. Pharmacodynamic Analysis

CCI

[figure not shown]
CCI

CCI

CCI

CCI

9. ASSESSMENT OF SAFETY

9.1. Safety Parameters

9.1.1. Demographic/Medical History

The Investigator or designee will collect a complete medical and surgical history at Screening and again at CRU admission to determine if any changes have occurred since Screening.

9.1.2. Vital Signs

Vital signs assessments will include respiratory rate (breaths per minute), systolic and diastolic BP (mmHg), and heart rate (HR) (beats per minute [bpm]) and body temperature, which will be measured after a participant has rested for at least 5 minutes in the supine position as per [Table 1](#), [Table 2](#), [Table 3](#), and [Table 4](#).

Any clinically significant abnormal vital sign assessment requires at least 1 repeat measurement.

Vital signs abnormalities that are (1) considered clinically significant initially and on confirmation, (2) require a participant to be discontinued from the study, (3) require a participant to receive treatment, or (4) require a change or discontinuation from the study drug (if applicable) will be recorded as AEs.

9.1.3. Weight and Height

Height will be completed at Screening only and weight as per [Table 1](#), [Table 3](#), and [Table 4](#).

9.1.4. Physical Examination

A full physical examination will be conducted at Screening. All subsequent physical examinations should be signs and symptoms driven. Full physical examination will include examination of the following: general appearance, head, ears, eyes, nose, throat, neck, skin, cardiovascular system, respiratory system, gastrointestinal system, musculoskeletal system, lymph nodes, and nervous system ([Table 1](#), [Table 3](#), and [Table 4](#)).

An abnormal physical examination finding during the on-study period (ie, following dose administration) that is considered clinically significant and (1) requires the participant to be discontinued from the study, or (2) requires the participant to receive treatment will be recorded as an AE.

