9.1.5. Electrocardiogram

Electrocardiograms (ECG) (12-lead) will be collected in triplicate within 5 minutes as per [Table 1](#), [Table 2](#), [Table 3](#), and [Table 4](#).

ECGs will be recorded after a participant has rested at least 5 minutes in the supine position. The following ECG parameters will be recorded: HR, PR, QRS, QT, and QTcF intervals.

ECG assessment will include interpretation of the tracings (eg, rhythm, presence of arrhythmia or conduction defects, any evidence of myocardial ischemia/infarction, or ST segment, T-wave, and U-wave abnormalities). The Investigator or designee is responsible for reviewing and over-reading the ECG interpretation, for assessing whether the ECG machine interpretation findings

are accurate, appropriate, normal, or abnormal, and for providing corrected interpretations as appropriate. In addition, any abnormal ECGs will be assessed for clinical significance.

Additional ECGs may be obtained if clinically indicated and must be obtained if abnormal and clinically significant or thought to be an error (eg, lead placement error, movement artifact, etc.). Any additional relevant data obtained by the Investigator during the course of this study will be supplied to the Sponsor.

For any ECG that the Investigator considers clinically significant, the Investigator will:

- Repeat the ECG.
- Follow-up ECG(s) will be obtained if any significant abnormalities are detected after dose administration to document resolution and as clinically indicated.
- Record as an AE any ECG that is 1) confirmed by the Investigator as clinically significant, 2) requires a participant to be discontinued from the study, or 3) requires a participant to receive treatment.

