10. ASSESSMENT OF SAFETY — ADVERSE EVENTS

10.1. Adverse and Serious Adverse Events

10.1.1. Definition of Adverse Events

An AE is defined as any untoward medical occurrence associated with the use of a drug in humans, whether or not considered related to the study drug. An AE can therefore be any unfavorable and unintended sign, symptom, or disease temporally associated with the use of a study drug. An AE may also constitute complications occurring as a result of protocol-mandated interventions (eg, invasive procedures such as biopsies), including the period prior to receiving the first dose of the study drug (eg, medication washout). In addition to new events, any increase in the severity or frequency of a pre-existing condition occurring after the participant signs the ICF is considered to be an AE. This includes any side effect, injury, toxicity, or sensitivity reaction.

A suspected adverse reaction is any AE for which there is a reasonable possibility that the drug caused the AE. For the purposes of expedited safety reporting, “reasonable possibility” means there is evidence to suggest a causal relationship between the drug and the AE. Suspected adverse reaction implies a lesser degree of certainty about causality than adverse reaction, which means any AE caused by a drug.

A life-threatening AE or life-threatening suspected adverse reaction is an AE or suspected adverse reaction that, in the view of either the Investigator or Sponsor, places the study participant at immediate risk of death. It does not include an AE or suspected adverse reaction that, had it occurred in a more severe form, might have caused death.

An AE or suspected adverse reaction is considered to be “unexpected” if it is not listed in the Reference Safety Information section of the current IB or is not listed at the specificity or severity that has been observed.

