10.2. Severity

Whenever possible, the severity of all AEs will be graded using the National Cancer Institute Common Terminology Criteria for Adverse Events (NCI CTCAE), Version 5.0.

For AEs not adequately addressed in the NCI CTCAE, Version 5.0, the following criteria should be used.

- Grade 1 – Mild: Asymptomatic or mild symptoms; clinical or diagnostic observations only; intervention not indicated.
- Grade 2 – Moderate: Minimal, local or noninvasive intervention indicated; limited age-appropriate instrumental activities of daily living (ADLs).
- Grade 3 – Severe: Medically significant but not immediately life-threatening; hospitalization or prolongation of hospitalization indicated; disabling; limiting self-care ADLs.
- Grade 4 – Life-threatening: Life-threatening consequences; urgent intervention indicated.
- Grade 5 – Fatal: Death.

To make sure that there is no confusion or misunderstanding between the terms “serious” and “severe”, which are not synonymous, the following note of clarification is provided. The term “severe” is often used to describe the intensity (severity) of a specific event (ie, mild, moderate, or severe); the event itself, however, may be of relatively minor medical significance (eg, severe headache). This is not the same as “serious”, which is based on the study participant/event outcome or action criteria associated with events that pose a threat to a participant’s life or functioning. Seriousness (not severity) serves as a guide for defining regulatory reporting obligations.

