10.5. Recording Adverse Events

10.5.1. General

All AEs will be recorded from the time the study participant signs the ICF form until the EOS Visit or ET Visit, whichever comes first. All AEs must be reported on the AE electronic case report form (eCRF) via the electronic data capture system. The Investigator is responsible for evaluating all AEs, obtaining supporting documents, and ensuring that documentation of the event is complete. Details of each reported AE must include at a minimum severity, relationship to study treatment, duration, and outcome. All serious and nonserious AEs must be followed until they are resolved or stabilized, or until reasonable attempts to determine resolution of the event are exhausted.

Any participant who experiences an AE may be discontinued from study treatment at any time at the discretion of the Investigator. The Sponsor/Medical Monitor(s) must be notified of the study participant discontinuation.

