10.5.3. Abnormal Laboratory Values

Clinically significant laboratory abnormalities will be recorded in the AE eCRF (eg, abnormalities that have clinical sequelae, more frequent follow-up assessments, or further diagnostic investigation). If the clinically significant laboratory abnormality is a sign of a disease or syndrome (eg, alkaline phosphatase and bilirubin 5 × ULN associated with cholecystitis), only the diagnosis (eg, cholecystitis) should be recorded in the eCRF.

If the clinically significant laboratory abnormality is not a sign of a disease or syndrome, the abnormality itself should be recorded on the eCRF. If the laboratory abnormality can be characterized by a precise clinical term, the clinical term should be recorded. For example, a serum potassium level of 7.0 mEq/L should be recorded as “hyperkalemia”.

Observations of the same clinically significant laboratory abnormality from visit to visit should not be repeatedly recorded on the AE eCRF, unless their severity, seriousness, or etiology changes.

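### Protocol 9.1.4 ties the recording of examination findings as AEs to treatment or study discontinuation, unlike the protocol's other AE rules, and nothing says which rule governs

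*Protocol*

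**What the plan says.** Protocol 9.1.4 deals with abnormal physical examination findings made after dosing. It calls for AE recording of a finding "that is considered clinically significant and (1) requires the participant to be discontinued from the study, or (2) requires the participant to receive treatment". SAP 3.12.5 repeats this wording.

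The other rules for turning an abnormality into an AE read differently:

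- **Vital signs (Protocol 9.1.2).** The list opens "Vital signs abnormalities that are (1) considered clinically significant initially and on confirmation, (2) require a participant to be discontinued from the study". It continues with treatment and with a change or stop of study drug, and the items are joined by *or*.
- **ECG (Protocol 9.1.5).** "Record as an AE any ECG that is 1) confirmed by the Investigator as clinically significant, 2) requires a participant to be discontinued" is followed by treatment, again joined by *or*.
- **Laboratory (Protocol 10.5.3).** "Clinically significant laboratory abnormalities will be recorded in the AE eCRF", with no treatment or discontinuation condition.
- **General definition (Protocol 10.1.1).** "An AE can therefore be any unfavorable and unintended sign, symptom, or disease temporally associated with the use of a study drug".
- **General recording rule (Protocol 10.5.1).** "All AEs will be recorded from the time the study participant signs the ICF form until the EOS Visit or ET Visit".

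The primary objective (Protocol 4.1, SAP 2.1.1) is safety and tolerability. SAP 7.17.1 summarizes TEAEs by participant and by event.

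**The concern.** The examination rule is the only one of the four assessment-specific rules that joins clinical significance to a consequence with *and*. A site that works from 9.1.4 would leave out a new, clinically significant sign that is only watched. A site that works from 10.1.1 and 10.5.1 would record it. Whether such an abnormality reaches the AE tables could then depend on how it was detected and on which section the investigator consulted.

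The study is small, descriptive and without formal tests (Protocol 11), so the AE tables carry much of the primary safety assessment. There is also less of a fallback for examination findings. Laboratory, vital sign and ECG data have their own summaries and listings (SAP 7.17.2 to 7.17.4), so an abnormality not entered as an AE can still be seen there. The visible text of SAP 7.17 plans no summary or listing of examination findings. Part of the SAP is redacted, so this can be said only of the visible text.

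**Working it through.** The plan states no figure on this point, so the check is a comparison of the rules followed by one line of arithmetic.

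**Step 1. The rules side by side.**

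| Source | Is clinical significance enough? | Treatment or discontinuation also needed? |
|---|---|---|
| Examination, Protocol 9.1.4 and SAP 3.12.5 | No | Yes (*and*) |
| Vital signs, Protocol 9.1.2 | Yes, if confirmed | No (*or*) |
| ECG, Protocol 9.1.5 | Yes, if confirmed | No (*or*) |
| Laboratory, Protocol 10.5.3 | Yes | No |
| General, Protocol 10.1.1 with 10.5.1 | Not even required | No |

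**Step 2. Trace one case.** Take a new sign found on a post-dose examination, judged clinically significant, watched but not treated, with the participant staying in the study. It can be an AE under 10.1.1, and 10.5.1 then requires it to be recorded. It does not meet the condition in 9.1.4. If the same sign led to study drug being stopped while the participant stayed in the study, it would still fall outside the literal wording of 9.1.4, which names discontinuation from the study only. The vital sign rule does cover a change or stop of study drug.

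**Step 3. Severity.** Where CTCAE v5.0 does not adequately cover an event, Protocol 10.2 describes Grade 1 as "Asymptomatic or mild symptoms; clinical or diagnostic observations only; intervention not indicated". A finding graded that way cannot meet the treatment condition of 9.1.4. The gap is not confined to Grade 1, because any clinically significant finding that is neither treated nor leads to study discontinuation is in the same position. Under the fallback scale, Grade 2 is described by a minimal intervention being indicated, so many of those findings would meet the treatment condition.

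**Step 4. Timing.** Section 9.1.4 covers post-dose findings only, while 10.5.1 starts at consent. TEAEs begin at the first dose (SAP 3.12.1), so this difference does not affect TEAE counts.

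**Step 5. Size.** Inputs: six participants (Protocol 11.1; SAP 3.5) and one participant whose finding is not recorded.

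- A SOC/PT row in which that participant has no other event: 0/6 = 0.0% against 1/6 = 16.7%, a difference of 16.7 percentage points.
- Overall TEAE rate, participant has no other TEAE: the rate is lower by 1/6 = 16.7 percentage points.
- Overall TEAE rate, participant has another TEAE: that participant is already counted, so the difference is 0 points and only the event count falls by one.

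**The case against.** The strongest answer is that 9.1.4 states when a finding will be recorded. It does not say that other findings will not be, and it does not claim to override Section 10. Sections 10.1.1 and 10.5.1 continue to apply, and 10.5.1 makes the investigator responsible for evaluating all AEs. A reader might infer from 9.1.4 that an examination finding becomes an AE only if it is treated or leads to discontinuation, and that Grade 1 findings are therefore lost. The documents do not support that. They support possible inconsistency, because no section tells a site which rule to follow.

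The exposed set is also narrow. Examinations after screening are prompted by signs and symptoms (9.1.4), so the prompting symptom can itself be recorded as an AE. Section 10.5.2 prefers a diagnosis to separate signs where one is known. AEs arising from vital signs, ECGs, laboratory values and reported symptoms are untouched.

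The laboratory comparison is not perfectly parallel, since 10.5.3 illustrates clinical significance by consequences. Those consequences include closer follow-up or further diagnostic work, however, which still falls short of treatment or discontinuation.

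The Grade 1 wording quoted above is a fallback and not the main grading scale. It shows how the gap arises but does not establish that all Grade 1 findings fall into it.

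These points limit the consequence. The difference in wording stands, as does the absence of a rule of precedence.

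**Conclusion.** The inconsistency is real and worth correcting; the loss of data is possible but not shown. Clinically significant examination findings that are neither treated nor lead to study discontinuation may be recorded inconsistently across up to three sites, and may be missing from the TEAE tables.

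The size is 16.7 percentage points for one of six participants in a given SOC/PT row, provided the participant has no other event in that row. For the overall TEAE rate it applies only if the participant has no other TEAE. Both statements assume a denominator of six; a larger enrolment would make the shift smaller. The documents give neither the frequency of such findings nor the share that would go unrecorded, so no probability can be attached.

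A reader might also describe this as damage to the primary endpoint. The text names safety and tolerability as the primary objective and defines no separate primary endpoint, so the effect is on the AE tables that serve that objective.

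**What to change.** 1. In Protocol 9.1.4 and SAP 3.12.5, use the structure of 9.1.2 and 9.1.5: record as an AE any abnormal examination finding that is (1) clinically significant, (2) requires discontinuation, or (3) requires treatment. Alternatively, add one sentence stating that 10.1.1 and 10.5.1 govern.
2. For consistency with 10.5.1 only, let the examination rule run from signature of the ICF. This does not change TEAE counts.
3. Before database lock, check clinically significant post-dose examination findings for a matching AE record, and query those without one. The documents do not say whether the eCRF flags examination findings as clinically significant, so the check may have to use source documents. It also covers Parts A and B, where dosing is complete (Protocol 3.3.2) and a wording change cannot act prospectively.

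The cost is a sentence in each document, one pre-lock check, and perhaps a few more low-grade events in the AE tables.
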